Recently, dentalAEGIS stated Ivoclar Vivadent's Adhese® Universal with VivaPen® as an effective delivery for all etching/adhesive methods; Tysowsky describes the characteristics of the material itself as technique-tolerant and predictable. It forms a stable and homogenous layer that is not sensitive to any application method. "Its hydrophilic solvent, which is acetone-free, provides for optimum wetting of the dentin and enamel, which leads to enhanced infiltration and optimum sealing of the dentinal tubules, preventing microleakage and associated postoperative sensitivity" (28). Although the role of in vitro data to predict clinical performance is increasingly recognised, randomised controlled trials (RCTs) remain the most rigorous study design for assessing the clinical effectiveness of an intervention, a health product or a medical device, especially when they are already commercially available. The majority of

studies investigating the clinical effectiveness of bonding systems use the longevity of restorations in NCCLs as the outcome (3). These are widely available and are normally used in clinical research, for assessment of adhesive systems (26,29) performance and efficacy, because NCCLs present no macro-mechanical retention, they present margins in enamel and/or dentin, and restorations are exposed to high stress during masticatory function (3,17), are located mainly in dentine, facilitating evaluation of the resin–dentine bond which is less stable than the resin–enamel bond (3).

The overarching goal of this RCT is to compare clinical performance at 24th month recall, of two MM adhesives from different manufactures, applied by SE or ER modes, with an SE-all-in-one adhesive (by SE or SE-EE modes) in NCCLs, using both USPHS and FDI criteria.

Objectives and Hypothesis

The purpose is to evaluate/compare clinical effectiveness of dual cure (DC) all-in–one Self-Etch (Futurabond®DC-FBDC) adhesive and the multimode (MM) (FuturabondU® -FBU- and Adhese®Universal –ADU-) adhesives, with or without selective enamel etching, in NCCL restorations, at 24th months follow-up, using Word Dental Federation (FDI) and United States Public Health Services (USPHS) criteria.

The null hypotheses are:

H0 – Bonding to NCCLs with FBDC by Self-Etch mode (FBDC-SE; G1) and MM adhesives by SE mode (MM-SE; G4G6) result in similar (no significant differences) clinical (aesthetic, functional and biologic) behaviour/performance;

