In this study will be included participants with clinical diagnosis of tooth structure coronal loss and needs for cervical (vestibular surface) restoration without chemical or bacterial origin, called non-carious cervical lesion (NCCL) located in pre-molars/molars (PM/M) teeth, with cavity dimensions defined in the study design. Therefore, restorations can be made in PM or M teeth; a participant can have up to 16 teeth (8PM + 8M) with NCCL. The number of teeth to restore by participant will be of maximum of 6 and a minimum of one NCCL, within this clinical trial. The allocation of the study arms (G1 to G6) to a particular tooth is randomly allocated, with the information available to the operator/principal investigator in sealed envelopes and previously prepared by the investigator-statistics. The allocation of the study arms (G1, G2, G3, G4, G5, G6) to each tooth by participant is performed randomly, but ensuring that the distribution of the groups is not repeated in the same participant. For this purpose, will be organized by the statistical investigator, 210 envelopes with 35 sequences of 6 study arms, where in each order of 6 groups is randomized.

If the patient has more than six teeth that meet the inclusion criteria, the selection of the PM and M teeth to be included in the clinical trial will be conducted randomly by scenarios randomized by the statistical investigator after participation and contact for the effect (not done a priori, since it is necessary 19448 scenarios prior randomization before observing any patient, whereas the possible teeth to be selected for treatment is between 6 and 16 and the teeth to select from 6).

The participant has as cost the academic/scientific fees, as in usual clinical context of Dentistry School Clinic of **Sector Sector** as "restoration of a tooth surface"/ by tooth to restore (One to six teeth), which of course would have to make even not participating in the investigation, as the Dentistry School Clinic fee scale.

The restorations included in this trial will be evaluated for determine clinical performance from baseline to 24th month by the three calibrated examiners. These observation appointments (three, in two years) as part of the clinical trial will be free of charges for participants. Baseline and 24th month data will be statistically analysing, according to this trial purpose and hypothesis.

2.3-STUDY ADHESION ARMS

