Study variable definition_- Clinical/direct observation and performance evaluation acceptance by means of FDI (*FDI World Dental Federation - clinical criteria for the evaluation of direct restorations*) (Adapted from (33) (Annex 3) and USPHS (34) (Annex 4).

2.7- DATA AND STATISTICAL ANALISYS PLAN (SAP)

Data statistical analysis and description according to aims of this trial; Specific program for statistical data analysis (IBM(c) SPSS(c) Statistics vs. 22 or later) will be used. The changes in parameters clinical performance (paired comparison analysis) by both, FDI and USPHS criteria will be assessed by McNemar or Wilcoxon tests, for both

primary and secondary outcomes, to determine differences between treatments with regard to aesthetic, functional and biological parameters from baseline to 24th month recall (longitudinal assessment). Differences will be considered to be significant at P<0.05. Whenever 3 groups will be compared at 24 months' recall, a Kruskal Wallis test will be used and upon significant differences detection, then Mann-Whitney tests considering Bonferroni correction will be used for pairwise group comparisons.

Comparison of FDI and USPHS acceptance (success rate) criteria evaluation outcomes for Esthetic, for Functional and for Biological Parameters, at 24th Month Follow-up, were compared using the chi-square test.

If missing data occurs, that is, if dropouts or non-observed due to loss of retention of the restoration, then the paired comparison will consider for the baseline just the restorations existing at the last moment (24 months).

2.8- OBSERVATIONS REGARDING SAMPLE CALCULATION

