It was assumed that the minimum number of adhesive restorations to be held in each of the six arms (G1 to G6) is 35 (210 restorations). The researchers did not have detailed information that allows the estimation of the sample size based on power analysis (the effect of the expected difference to the end of the time considered for the study). Thus, in principle they assumed the rules of thumb, usually considered in research situations where there is no advance information concerning the performance evaluation of these adhesive medical devices available on the market, using this assay. Moreover, when considering a "simple" analysis comparison using a McNemar test (repeated measures) in six groups would be necessary in total, including at least 80 cases (to restore teeth) in the sample. When considering at least 35 restorations by group, researchers are greatly increasing the minimum number stipulated in the aforementioned technique. In addition, clinical studies previously performed on this issue (between 2004 and 2012) relative to the post-market clinical evaluation performance of adhesive products/use mode in NCCLs, in the context of restorative dentistry field, has enabled to measure a minimum of 30 restorations as viable for determining events in a short/mean-term as the clinical performance evaluation of a similar nature of adhesives.

2.9- GOOD CLINICAL PRACTICE FOR CLINICAL RESEARCH

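### The plan glosses 'similar' as absence of significance and plans no between-arm difference or confidence interval, so a non-significant result at 35 restorations per arm has no other stated reading

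*Combined protocol and SAP*

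**What the plan says.** The section Objectives and Hypothesis lists ten null hypotheses. Three concern overall performance: G1 against G4 and G6, G2 against G3 and G5, and the comparison by adhesive. Each states that the adhesives "result in similar (no significant differences) clinical (aesthetic, functional and biologic) behaviour/performance". Six more, on success and retention, use 'similar' without the bracketed words. The tenth compares the FDI and USPHS criteria.

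Section 2.7 gives one criterion: "Differences will be considered to be significant at P<0.05". For three-group comparisons at 24 months, "a Kruskal Wallis test will be used and upon significant differences detection, then Mann-Whitney tests considering Bonferroni correction will be used". McNemar and Wilcoxon tests cover change from baseline, and a chi-square test compares the two sets of criteria. The section mentions no between-arm effect estimate, confidence interval or reading of a non-significant P value.

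Section 2.8 sets a minimum of 35 restorations per arm and says that the researchers "did not have detailed information that allows the estimation of the sample size based on power analysis". It supports the number with a remark that "a McNemar test (repeated measures) in six groups would be necessary in total, including at least 80 cases", and with earlier studies whose experience "has enabled to measure a minimum of 30 restorations as viable". Section 2.2 provides "210 envelopes with 35 sequences of 6 study arms" and allows one to six restored teeth per participant.

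**The concern.** A null hypothesis is a statement about the population, whereas statistical significance describes what one sample showed. Putting the second inside the first makes failure to reject look like the definition of similarity. Nothing later in the plan corrects this, because no planned output would show how large a difference the data still allow.

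The adhesives are already on the market, and the stated purpose is to compare their clinical effectiveness. If a P value above 0.05 is written up as similar performance, readers may treat the products or etching modes as interchangeable when the trial was only imprecise.

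**Working it through.** **The plan's own figure.** The 80 cases in section 2.8 refer to a McNemar test and come without alpha, power or discordant proportions, so they can be neither reproduced nor refuted. The usual formula is n = [1.96·√pd + 0.842·√(pd − d²)]² / d², with two-sided alpha 0.05, 80% power, discordant proportion pd and difference d.

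- pd = 0.10, d = 0.10: (0.620 + 0.252)² / 0.01, giving 77.
- pd = 0.25, d = 0.15: (0.980 + 0.401)² / 0.0225, giving 85.

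Other pairs of inputs give from 14 to 234. In any case a McNemar test of change within an arm says nothing about precision between arms.

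**Inputs for the between-arm check.** From the plan: 35 restorations per arm; 35 + 35 = 70 per adhesive when pooled (G1G2, G3G4, G5G6); Kruskal-Wallis at 0.05; then Bonferroni-corrected Mann-Whitney. My assumptions: a binary outcome (success or retention), two-sided tests, three pairs (0.05/3 = 0.0167), independent restorations, no losses, two arms at the reference rate and one worse. The documents give no success rates, so 80% to 95% is an assumed range.

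**Method.** For a binary outcome the tie-corrected Kruskal-Wallis statistic equals (N − 1)/N times Pearson's chi-square for the 3 × 2 table. It is compared with 5.99. The squared Mann-Whitney z is the same expression for a 2 × 2 table, and |z| is compared with 2.39. Power is the exact sum of binomial probabilities over all tables that reject. The pairwise figures ignore the requirement that Kruskal-Wallis reject first, which can only lower them.

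**Power (%) for a deficit of 10 / 15 points**

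| Reference rate | Kruskal-Wallis, 35 each | Corrected Mann-Whitney, 35 each | Kruskal-Wallis, 70 each | Corrected Mann-Whitney, 70 each |
|---|---|---|---|---|
| 95% | 29.4 / 53.8 | 12.4 / 29.0 | 56.4 / 85.0 | 35.0 / 65.3 |
| 90% | 22.0 / 41.2 | 9.5 / 21.0 | 40.2 / 70.6 | 23.2 / 49.0 |
| 85% | 18.1 / 34.0 | 7.9 / 17.7 | 32.5 / 60.9 | 17.9 / 39.9 |
| 80% | 15.8 / 29.6 | 7.4 / 15.9 | 27.9 / 54.3 | 15.1 / 34.4 |

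The miss rate is 100 minus power. At a 95% reference rate:

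- 35 per arm, Kruskal-Wallis: 71% and 46%.
- 35 per arm, corrected pairwise: 88% and 71%.
- 70 per adhesive, Kruskal-Wallis: 44% and 15%.
- 70 per adhesive, corrected pairwise: 65% and 35%.

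**What one non-significant result would hide.** Take 33/35 against 30/35. The difference is 3/35 = 0.086 and the pooled proportion is 63/70 = 0.9.

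- Chi-square = 0.0857² / (0.9 × 0.1 × 2/35) = 1.429. Times 69/70 this is 1.408, so z = 1.19 and the Mann-Whitney P = 0.24.
- Wilson limits are 0.814 to 0.984 and 0.706 to 0.937.
- Newcombe lower limit: 0.086 − √(0.129² + 0.080²) = −0.07.
- Newcombe upper limit: 0.086 + √(0.041² + 0.151²) = 0.24.

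The result is non-significant, yet the interval runs from −7 to +24 points.

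**The case against.** The strongest reply is that the bracketed words are loose phrasing of a null hypothesis. A reader might infer that the plan commits itself to reporting every P of 0.05 or more as demonstrated similarity. It does not: no sentence says so, and section 2.7 states only when a difference counts as significant. The gloss is also confined to the three performance hypotheses. What stands is that the plan gives no other way to read a non-significant result.

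A reader might also infer that differences of 10 to 15 points would usually be missed throughout the trial. That goes too far. At a 95% reference rate, Kruskal-Wallis at 35 per arm detects a 15-point deficit slightly more often than not, and the pooled contrasts detect it 85% of the time. At a 98% reference rate, power at 35 per arm rises to about 41% and 68%. Fisher's test would give a bleaker picture (86% and 67% missed at 95% against 85% and 80%), but the plan does not use it.

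Nor does the plan foresee nothing but P values: Annex 3 calls for counts and percentages of acceptable restorations. What is missing is the between-arm difference and its interval.

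Finally, the performance hypotheses may be tested on ordinal scores. Power for those depends on score distributions that the documents do not give.

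**Conclusion.** The concern holds as a gap in interpretation and reporting. The plan supplies a P value threshold, a gloss that ties similarity to non-significance, and no estimate with an interval to show what a non-significant result excludes.

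The gap matters most for the 35-per-arm contrasts. There a 10-point deficit is missed in most trials on either planned test, across the assumed 80% to 95% range. For a 15-point deficit that is true throughout the range only of the corrected pairwise test. For the pooled contrasts the risk is smaller but not negligible.

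The sizes rest on assumed success rates, one arm being worse than two equal ones, independence, and complete follow-up of exactly 35 restorations, which is the stated minimum. If the third arm lies midway, Kruskal-Wallis power at 95% falls to 20% and 38%. With 28 per arm (an assumed 20% loss) and one arm worse, it is about 22% and 42%. Correlation between teeth of one patient could move precision either way, because arms are not repeated within a patient.

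**What to change.** 1. In the three performance hypotheses, delete the bracketed words as the meaning of 'similar'.
2. In section 2.7, for each between-arm contrast at 24 months, add the difference in proportions (or an odds ratio for ordinal scores) with a 95% confidence interval that allows for several teeth per patient, for example from GEE or cluster-robust standard errors.
3. State that P of 0.05 or more will be reported as 'no difference shown', together with the interval, and not as similar performance.

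This needs no equivalence margin, extra participants or new data. The clustered interval takes modest extra analysis beyond the listed tests. The other cost is a more cautious conclusion when intervals are wide.

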H0 – Bonding to NCCLs with FBDC-SE (G1) and MM-SE(G4G6) result in similar restorations (aesthetic, functional and biologic) success rates;

H0 – Bonding to NCCLs with FBDC-SE (G1) and MM-SE (G4G6) adhesives result in similar restoration retention rates;

H0 – Bonding to NCCLs with FBDC by SE and enamel etching mode (FBDC-SE-EE; G2) and MM adhesives by Etch-and-Rinse mode (MM-ER; G3G5) result in similar (no significant differences) clinical (aesthetic, functional and biologic) behaviour/performance;

H0 – Bonding to NCCLs with FBDC-SE-EE (G2) and MM-ER (G3G5) result in similar restorations (aesthetic, functional and biologic) success rates;

H0 – Bonding to NCCLs with FBDC-SE-EE (G2) and MM-ER (G3G5) result in similar restoration retention rates;

H0 – Bonding to NCCLs with FBDC (G1G2) or FBU (G3G4), DC adhesives, and ADU (G5G6) light-curing adhesive, with SE or SE-ER/ER modes result in similar (no significant differences) clinical (aesthetic, functional and biologic) behaviour/performance;

H0 – Bonding to NCCLs with FBDC (G1G2) or FBU (G3G4) and ADU (G5G6) lightcuring adhesive, with SE or SE-ER/ER modes result in similar restorations (aesthetic, functional and biologic) success rates;

H0 – Bonding to NCCLs with FBDC (G1G2) or FBU (G3G4) and ADU (G5G6) lightcuring adhesive, with SE or SE-ER/ER modes result in similar restoration retention rates;

H0 - FDI or USPHS criteria evaluation outcomes not differ for the same data, at 24th month follow-up.

2 – POPULATION, MATERIALS AND METHODS

2.1- TRIAL DESIGN

The trial design follows the Consolidated Standards of Reporting Trials (CONSORT) statement (30). Prospective, double blind, clinical trial; randomized allocation of NCCL restorations by six adhesion interventional groups (6 arms) for examination of restorations performance.

Study will take place in University

Dentistry School Clinic. Participants recruitment between November 2015 and April 2016. Restorations estimated to be done until April or May 2016 year.

-

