Study adhesive NCCLs restorations are randomly distributed to 6 groups (6 arms/interventions), according to adhesive (product) and adhesion mode (SE, ER) of use, as show in table 1.

procedures.		
Control and study Groups and NCCL restoration distribution (n)	Adhesives System_Mode	Application Procedures
G1 (Control group) n=35	FBDC_SE	Mixture Liquid 1 into Liquid 2 (1:1 ratio). Apply and rub this homogeneous mixture to enamel and dentine for 20 seconds; Air-blow for 5 seconds; light cure (1000mW/cm2), for 20 seconds.
G2 (Control group) n=35	FBDC, SE with enamel etching (FBDC_SE-EE)	Apply etchant selectively on enamel and leave for 30 seconds. Thoroughly rinse for 1 minute and gently dry. Dentine surface must slightly remain wet. Mixture Liquid 1 into Liquid 2 (1:1 ratio). Apply and rub this homogeneous mixture to enamel and dentine for 20 seconds; Air-blow for 5 seconds; light cure (1000mW/cm2), for 20 seconds.
G3 n=35	FBU_ER	Apply etchant for 30 seconds on enamel and 15 seconds on dentine; Thoroughly rinse for 1 minute and gently dry. Dentine surface remain with silky matt appearance. Apply and rub adhesive for 20 seconds, and air-blow for 5 seconds; light-cured (1000mW/cm2) for 20 seconds.
G4 n=35	FBU_SE	Apply and rub adhesive for 20 seconds, and air-blow for 5 seconds; light-cured (1000mW/cm2) for 20 seconds.
G5 n=35	ADU_ER	Apply etchant for 30 seconds on enamel and 15 seconds on dentine; Thoroughly rinse for 1 minute and gently dry. Dentine surface remain dry. Scrubbed adhesive for at least 20 seconds; Air-blow to disperse adhesive until a glossy, immobile film layer results; Light-cure (1000mW/cm2) for 20 seconds.
G6 n=35	ADU_SE	Scrubbed adhesive for at least 20 seconds; Air-blow to disperse adhesive until a glossy, immobile film layer results; Light-cure (1000mW/cm2) for 20 seconds.
FBDC: Futurabond [®] DC; FBU: F	uturabond [®] U; ADU:	Adhese® Universal; SE: Self-Etch; ER: Etch-and-Rinse

Table 1 - Control (G1, G2) and study arms/ groups (G3, G4, G5, G6) of NCCL restorations randomized allocated according to adhesion mode and application procedures

2.4- OPERATOR / EXAMINERS CALIBRATION

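### The pooled product nulls set FBDC with no dentine etched against FBU and ADU with dentine etched in half the restorations, and no planned analysis separates adhesive from etching

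*Combined protocol and SAP*

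**What the plan says.** The nulls in Objectives and Hypothesis are unnumbered; I count them in the order listed.

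- **Nulls 1–3** compare FBDC and the multimode adhesives in self-etch mode, for example "FBDC-SE (G1) and MM-SE (G4G6) adhesives result in similar restoration retention rates".
- **Nulls 4–6** compare FBDC with enamel etching and the multimode adhesives in etch-and-rinse mode: "FBDC-SE-EE (G2) and MM-ER (G3G5) result in similar restoration retention rates".
- **Nulls 7–9** pool each product over its two modes: "FBDC (G1G2) or FBU (G3G4) and ADU (G5G6) lightcuring adhesive, with SE or SE-ER/ER modes result in similar restoration retention rates". Null 7 also labels the products by cure type: "FBDC (G1G2) or FBU (G3G4), DC adhesives, and ADU (G5G6) light-curing adhesive".
- **Null 10** compares the FDI and USPHS criteria and is not affected.

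The purpose statement says that FBDC and the multimode adhesives are compared "with or without selective enamel etching, in NCCL restorations".

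Table 1 (section 2.3) gives G2 the instruction "Apply etchant selectively on enamel and leave for 30 seconds" and gives G3 and G5 "Apply etchant for 30 seconds on enamel and 15 seconds on dentine". G1, G4 and G6 receive no etchant. All six arms are light-cured for 20 seconds at 1000 mW/cm2.

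For three-group comparisons at 24 months, section 2.7 plans a Kruskal-Wallis test followed by Bonferroni-corrected Mann-Whitney tests. The other tests listed are McNemar, Wilcoxon and chi-square.

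**The concern.** Each product has one unetched and one etched arm, so pooling looks balanced. It is not, because the etched arm differs between products: FBDC has enamel etched only, while FBU and ADU have enamel and dentine etched. A pooled FBDC contrast therefore mixes the adhesive with the dentine step.

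The protocol gives reasons to take that step seriously. The Introduction chooses NCCLs because they lie mainly in dentine and so test the dentine bond, and it argues that strong-acid demineralisation can reduce chemical bonding by 10-MDP.

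If dentine etching matters, its effect could be reported as a product difference. If it runs against a real product difference, the two could cancel and the products be reported as similar. The purpose statement also leads a reader to expect evidence on multimode adhesives with selective enamel etching, which no arm provides.

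**Working it through.** **Inputs.** Six arms of 35 restorations (sections 2.2 and 2.8): 6 × 35 = 210, which reproduces the stated total. Etching by arm is from Table 1. Section 2.8 says there was no information for a power analysis, so success rates and the etching effect below are my assumptions.

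**Etching by arm**

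| Arm | Product | Enamel etched | Dentine etched |
|---|---|---|---|
| G1 | FBDC | no | no |
| G2 | FBDC | yes | no |
| G3 | FBU | yes | yes |
| G4 | FBU | no | no |
| G5 | ADU | yes | yes |
| G6 | ADU | no | no |

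Pooled by product, enamel is etched in 50% of each. Dentine is etched in 0/70 FBDC, 35/70 FBU and 35/70 ADU restorations.

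**What each contrast estimates.** Let *a* be the product effect, *e* the enamel-etching effect and *δ* the dentine-etching effect, taken as additive.

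- Nulls 7–9, FBU − FBDC: [a(FBU) + (e + δ)/2] − [a(FBDC) + e/2] = a(FBU) − a(FBDC) + δ/2. ADU − FBDC has the same form.
- Nulls 4–6, G3 − G2: a(FBU) − a(FBDC) + δ. From G2, G3 and G5 alone, neither FBDC product contrast is estimable.
- Nulls 1–3, G4 − G1: a(FBU) − a(FBDC), with no etching term.
- Pooled FBU − ADU: a(FBU) − a(ADU), because δ/2 cancels.

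Cancellation example: if ADU were truly 5 points better than FBDC and dentine etching cost 10 points, the pooled contrast would be 5 − 10/2 = 0.

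**False-difference rate under the planned tests.** I assumed identical adhesives, 95% success without dentine etching, 95% − d with it, and independent restorations. I simulated three pooled groups of 70 and counted a Kruskal-Wallis P<0.05 followed by at least one FBDC pair significant at 0.05/3.

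| d (points) | Expected pooled FBDC difference, d/2 | False FBDC difference, nulls 7–9 |
|---|---|---|
| 0 | 0 | 2% |
| 5 | 2.5 | 5% |
| 10 | 5 | 14% |
| 15 | 7.5 | 28% |

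Treating G2, G3 and G5 as three groups of 35 in the same way gives about 5%, 21% and 44% at d = 5, 10 and 15. Those would be correct findings about strategies; they mislead only if read as findings about the adhesive.

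**Could a model separate the effects?** A six-arm additive model has 5 parameters and rank 5, so yes. With product-by-etching interaction it has 7 parameters and rank 6, and *δ* is no longer estimable. With unit variance per restoration, the additive FBU − FBDC contrast has variance 0.050, against 1/35 + 1/35 = 0.057 from the self-etch arms alone. The standard-error ratio is √(0.050/0.057) ≈ 0.94, so the model gains little precision for its added assumption.

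**The case against.** The strongest reply is that the contrast is declared. The overarching goal in the Introduction lists SE or ER modes for the multimode adhesives and SE or SE-EE modes for FBDC. Nulls 4–6 name the mode on each side, and section 2.3 defines the arms by product and mode. This stands: nulls 4–6 are sound as comparisons of adhesive plus mode. A reader might infer that they are invalid; the documents do not support that.

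A reader might also infer that the trial cannot compare the adhesives at all. It can. Nulls 1–3 use arms without etchant and isolate the adhesive in self-etch mode, and FBU versus ADU has matching modes. Nor is separation impossible in principle: the six-arm additive model achieves it if products do not interact with etching. However, section 2.7 plans no such model, and the Introduction itself reports laboratory performance of universal adhesives as material-dependent.

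The size of the effect is unknown and may be small. The Introduction cites an 18-month NCCL study of another universal adhesive in which retention did not depend on bonding strategy, and modes differed only in marginal adaptation by FDI criteria. That weakens any claim of a large effect on retention. It does not repair a contrast built to include the effect.

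On cure type, a reader might infer that light-curing every arm contradicts the dual-cure label. It does not, since the label describes the material. Only null 7 applies that label; nulls 8–9 merely describe ADU as light-curing.

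**Conclusion.** The point holds for nulls 7–9: each FBDC product contrast contains half of any dentine-etching effect, and the planned tests cannot remove it. Under additivity, this follows from Table 1 without any assumed rate. Nulls 4–6 stand as strategy comparisons but cannot support a conclusion about the adhesive alone. Nulls 1–3 and pooled FBU versus ADU are unaffected.

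The rates of about 5%, 14% and 28% are illustrations. They rest on 95% success, identical adhesives, independent restorations and assumed losses of 5, 10 and 15 points; the documents give neither the size nor the sign of the effect. They do not show that a false difference is likely.

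Two smaller mismatches also need attention. The purpose statement implies selective enamel etching for the multimode adhesives, which Table 1 does not provide. Null 7 invites a cure-type conclusion that the design cannot give: the two products labelled dual-cure come from one manufacturer and the light-curing one from another (Table 2), and every arm is light-cured.

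**What to change.** 1. Base FBDC-versus-multimode adhesive conclusions on the self-etch arms: G1, G4 and G6.
2. Keep pooled FBU versus ADU (G3G4 versus G5G6).
3. State that no adhesive conclusion will be drawn from the pooled FBDC contrasts in nulls 7–9. If a six-arm model with product and etching terms is added as support, state its no-interaction assumption.
4. State that nulls 4–6 compare strategies, adhesive plus etching pattern.
5. Reconcile the purpose statement with Table 1, so that it is clear that selective enamel etching is studied for FBDC only.
6. Draw no cure-type conclusion from null 7.

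These are changes to the purpose, the nulls and section 2.7 only; no arm, procedure or visit changes. The cost is precision: FBDC contrasts rest on 35 rather than 70 restorations per product. At 95% success and with independent restorations, the standard error of a difference rises from √(2 × 0.95 × 0.05/70) = 3.7 points to √(2 × 0.95 × 0.05/35) = 5.2 points.
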